6b Choice of Comparator: Control participants will receive placebo capsules containing 288 mg of rice protein (California Natural Products, Lathrop, CA), 109.3 mg microcrystalline cellulose (Stauber USA, Fullerton, CA), 4.3 mg Aerosil® 200 fumed silica (Vivion Inc., San Carlos, CA), and 4.3 mg magnesium stearate (Nitika Pharmaceutical Specialties, Maharashtra, India), and formulated into a capsule by Metagenics, Inc. (Gig Harbor, WA).

7 Objectives

A methodological limitation of assessing the efficacy of CD treatments is that the gut microbiome of CD subjects is highly personalized in terms of state and dynamics. By correlating time-resolved fluctuations in the gut microbiome of CD subjects with their concomitant changes in the profile of XN metabolites, BA profiles, and other markers of gut microbiome-associated biochemical activity as well as with established surrogate end-points of the disease, we hypothesize:

1) XN at the given dose will be safe and tolerable in adults with active CD;

2) XN will improve biomarkers and improve the Crohn's Disease Activity Index (CDAI) an activity index of CD activity;

3) We can identify a biological signature(s) of XN through its metabolic byproducts in blood, urine, and stool as well as its effect on bile acid reabsorption; and

4) Specific biological signature(s) of XN exposure will uniquely contribute to changes in CD-associated disease activity indices.

To test these hypotheses and generate a conceptual model, we define four Specific Aims:

Protocol

- Aim 1. Determine the clinical safety and tolerability of xanthohumol in adults diagnosed with CD. We will determine the safety and tolerability of xanthohumol in adults diagnosed with CD over 8 weeks in a Phase 2 trial. The primary hypothesis is that in the XN arm, the number of participants with an adverse event or abnormal lab value will not be more than 50% higher than the number in the placebo group.
- Aim 2. Assess changes in levels of inflammation and symptom severity related to CD.

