A sample size of 12 per group provides 80% power to detect a 50% difference in proportions of participants between groups by chi2 test experiencing a laboratory abnormality or adverse event at a significance threshold of α =0.05. In addition, based on our preliminary trial data for change in TNF- α , and applying a 2-sided t-test of means, n=24 allows for n=12 per arm and provides >90% power, at a significance threshold α =0.05, to detect a mean change of -0.5 =/- 0.25 pg/ml in XN-treated participants with CD, based on an estimated mean change of 0.1 +/- 0.25 pg/ml from placebo. Will we randomize up to 32 participants to allow for attrition up to 25% [resulting in a final sample of at least n=24/arm.

Based on our preliminary trial data for change in TNF- α , and applying a 2-sided t-test of means, n=24 allows for n=12 per arm and provides >90% power, at a significance threshold α =0.05, to detect a mean change of -0.5 =/- 0.25 pg/ml in XN-treated participants with CD, based on an estimated mean change of 0.1 +/- 0.25 pg/ml from placebo. Will we randomize up to 32 participants to allow for attrition up to 25% [though we had <10% attrition in our previous trial in this population] resulting in a final sample of at least n=24/arm.

15 Recruitment

Participants will be recruited from the region via posted fliers and the NUNM clinic via posted fliers and IRB-approved mailings to current patients. Members of the study team will present information about study participation to CD support and community groups and set out flyers for attendees to pick up. In addition, we will use Craigslist and social media (i.e. Facebook and Instagram) as well as the NUNM weekly newsletter. Candidates from the community would

simply respond to a dedicated study telephone line or email, and express their interest, and are then contacted by a Study Coordinator.

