Laboratory measures (including red blood cell count, white blood cell count, hematocrit (%), hemoglobin, mean corpuscular volume, AST, ALT, creatinine-estimated glomerular filtration rate (eGFR), blood urea nitrogen (BUN), and creatinine) will be analyzed by first assessing descriptive statistics including mean, median and standard deviation. All distributions will be tested for skew and transformed (e.g., natural log transformed) as needed to reduce the influence of skew in subsequent analyses. All parameters will be evaluated by formally comparing means from baseline

Protocol

to each time point by unpaired, 2-sided t-tests, as well as for trends over time by applying linear mixed ANOVA models with time point as a repeated factor.

As an element of the evaluation for safety of the intervention, the % laboratory newly abnormal (for values within the clinically normal range at baseline) per clinical laboratory reference ranges for each lab parameter will be reported at each 2-week time point and the % compared between XN and placebo groups by Fisher's exact test.

Assessment for changes in the distribution of each lab parameter will be performed by presenting means and confidence intervals (CI) for the change in each group, as well as the mean CI for the difference between groups; significance will be tested using 2-sided, unpaired t-tests (or, if inspection of distributions indicates strong non-normality, with a non-parametric Wilcoxon signed rank test) of the mean values for XN compared to placebo.

Assessment for overall *increases* or *decreases* in parameters of interest will be tested for linear trends of the means by linear mixed ANOVA with time point as a repeated factor, which may be suggestive of evidence for cumulative toxicity if trending in a clinical deleterious direction.

Analysis of inflammatory cytokines, gut permeability biomarkers, and endotoxemia:

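### Section 14's 80% power is for an absolute difference of about 50 percentage points and does not support Aim 1's relative 50% limit; the final sample is 24 in total, not 24 per arm

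*Protocol*

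**What the plan says.** Section 14 (Sample Size) bases the primary safety objective on this sentence: "A sample size of 12 per group provides 80% power to detect a 50% difference in proportions of participants between groups by chi2 test". The endpoint is at participant level, namely "experiencing a laboratory abnormality or adverse event", and the test is made "at a significance threshold of α =0.05". No placebo rate is given, and the sidedness of the chi-square test is not stated. The section then takes 24 participants as 12 per arm, randomises up to 32 to allow for up to 25% attrition, and ends, twice, with "resulting in a final sample of at least n=24/arm".

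Section 7, Aim 1 words the primary hypothesis as an upper limit on a ratio: the number of XN participants with an adverse event or abnormal laboratory value "will not be more than 50% higher than the number in the placebo group".

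Section 20a names one between-group test for proportions. Newly abnormal results "for each lab parameter will be reported at each 2-week time point", with "the % compared between XN and placebo groups by Fisher's exact test". It names no test for the composite of laboratory abnormality or adverse event.

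**The concern.** The same figure, 50%, appears in Section 14 as the difference to be detected and in Aim 1 as the largest tolerable relative excess. A reader will take the first as the power calculation for the second. The two agree only when the placebo rate is 100%, because half the placebo rate equals 50 points only there. At any rate where a 1.5-fold increase is possible (up to about 67%), Aim 1's limit is a much smaller difference than the one powered.

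The direction differs too. Aim 1 claims that an excess is not too large; Section 14 powers a test to detect a difference. If the sample has little chance of detecting a 1.5-fold excess, a non-significant result says little about whether Aim 1 is true. What is at stake is how a null safety comparison is read.

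Separately, the closing figure of Section 14 doubles the evaluable sample.

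**Working it through.** **Inputs.** From Section 14: 12 per arm, alpha 0.05, 80% power, chi-square, 32 randomised, up to 25% attrition. From Aim 1: a limit of 1.5 times placebo. Assumptions: a two-sided test, and placebo rates scanned because none is stated.

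**1. Final sample.** 32 × (1 − 0.25) = 24 in total, and 24 / 2 = 12 per arm. A final 24 per arm is 48 completers, which at 25% attrition needs 48 / 0.75 = 64 randomised. With 32 randomised there are at most 16 per arm even with no attrition.

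**2. Reproducing the 80%.** The normal approximation is power = Φ{[|p2 − p1|√n − 1.96√(2p̄(1 − p̄))] / √(p1(1 − p1) + p2(1 − p2))}, where p̄ is the mean of the two rates.

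For 5% against 55%, n = 12: 0.50 × √12 = 1.732; 1.96 × √(2 × 0.30 × 0.70) = 1.270; √(0.0475 + 0.2475) = 0.543. So (1.732 − 1.270) / 0.543 = 0.85 and power is 80.2%. The plan's figure is reproduced for a 50-point difference at a low placebo rate.

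Exact power is the sum of the binomial probabilities of all 13 × 13 tables with p ≤ 0.05. At 12 per arm, for a 50-point difference:

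| Placebo vs XN | Chi-square | Fisher |
|---|---|---|
| 5% vs 55% | 83% | 69% |
| 10% vs 60% | 79% | 64% |
| 25% vs 75% | 77% | 61% |
| 40% vs 90% | 79% | 64% |

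**3. The relative limit in Aim 1.** The same exact method, 12 per arm, XN rate = 1.5 × placebo rate:

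| Placebo vs XN | Chi-square | Fisher |
|---|---|---|
| 20% vs 30% | 8% | 3% |
| 30% vs 45% | 13% | 6% |
| 40% vs 60% | 19% | 10% |
| 50% vs 75% | 26% | 14% |
| 60% vs 90% | 39% | 23% |
| 67% vs 100% | 61% | 37% |

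The last row is the ceiling, since 1.5 times any higher rate exceeds 100%. A one-sided test does not rescue the relative reading: the normal approximation then gives 14-52% at placebo rates of 20-60%, and 73% at the ceiling.

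**4. Aim 1 read as non-inferiority.** With equal true rates p and margin m = 0.5p, one-sided 0.025 and 80% power, n per arm = (1.96 + 0.842)² × 2p(1 − p) / m². For p = 40%: 7.85 × 0.48 / 0.04 = 94.2, so 95 per arm. The same formula gives 252 at 20%, 63 at 50% and 42 at 60%.

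**5. What a null result would show.** Suppose 6 of 12 are affected in each arm. The standard error of the log ratio is √(2 × (1 − 0.5) / (0.5 × 12)) = 0.408. The 95% interval for the ratio is exp(±1.96 × 0.408), or 0.45 to 2.23. The observed rates are identical, yet 1.5 is well inside the interval.

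**The case against.** Four points can be made for the plan.

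First, the 80% is not an arithmetic error. For 50 points by uncorrected chi-square it is met or exceeded at placebo rates of 5% or less, and 77-79% at 10-40% is close to it. This stands; the fault is that the effect powered is not the one Aim 1 names.

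Second, a reader might infer from Section 20a that the primary comparison will use Fisher's exact test, so that the real power is 61-64%. The protocol does not support that. Section 20a assigns Fisher's test to each laboratory parameter at each visit; it covers neither adverse events nor the participant-level composite. Chi-square is the only test this document attaches to the composite, and the statistical analysis plan, not shown, may name its final test. The 61-64% is therefore conditional.

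Third, a reader might infer from 24 per arm that the trial has more than 90% power for 50 points (Fisher would give 93-96% at placebo rates of 10-40%). No stated power uses that size: both power statements in Section 14 are tied to 12 per arm, and the total of 32 is consistent elsewhere. It is a slip, though a repeated one.

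Fourth, 12 per arm is the worst case, since Section 14 reports attrition below 10% in an earlier trial. With 16 per arm, chi-square power for 50 points is 85-90% at placebo rates of 10-40%. For the 1.5-fold increase, however, Fisher's power is still only 4-36% at placebo rates of 20-60%.

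It would also go too far to say that power for the relative limit is below 25% everywhere: that holds for Fisher's test at placebo rates of 20-60%, but it reaches 37% at 67% against 100%.

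**Conclusion.** The point holds on two counts. The final sample is misstated by a factor of two, in two places, and this depends on no assumption. The stated power does not support the primary hypothesis: against Aim 1's limit, 12 per arm gives 8-39% by chi-square or 3-23% by Fisher at placebo rates of 20-60%, with ceilings of 61% and 37%, so 80% is not reached at any placebo rate. These figures assume a two-sided 0.05 test and a scanned placebo rate. Because Aim 1 is a claim of no material excess, a non-significant difference would not establish it.

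The mismatch between chi-square and Fisher is a lesser matter of consistency: the document names no test for the composite in Section 20a, and power for 50 points falls to 61-64% (placebo rates 10-40%) only if Fisher's test is used for it. The TNF-α calculation is not in question: a difference of 0.6 with SD 0.25 and 12 per arm gives more than 99.9% power, consistent with the plan's claim of over 90%.

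**What to change.** - In Section 14, replace the final sample of 24 per arm with 24 in total (12 per arm), in both places.
- State that the 80% is for an absolute difference of about 50 percentage points by uncorrected chi-square, and give the assumed placebo rate and the sidedness.
- State that power for the 50% relative limit in Aim 1 is far below 80% (8-39% by chi-square at placebo rates of 20-60%). Say that Aim 1 will be reported as an estimate of the between-arm contrast with its confidence interval, and that a non-significant test will not be taken as establishing it.
- Name the same test for the composite in Sections 14 and 20a. If it is Fisher's, restate the power for 50 points as 61-64% at placebo rates of 10-40%.

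These are wording changes and need no more participants. The cost is a less favourable power statement and a more modest claim for the primary safety objective.

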Because Black/African Americans are under-represented in the Portland metro area, we will specifically target recruitment strategies to reach Black/African Americans in the region.

No NIH-defined children will be enrolled.

Assignment of interventions (for controlled trials) Allocation

16a Sequence generation

Randomization will occur in up to 8 blocks of 4 based on biological sex. Initial randomization series will be generated using readily available random sequence generators designed to do so such as Randomization.com, which allows for block randomization.

16 b Allocation Concealment mechanism

Envelopes will be opaque and signed across the seal. The randomization "code" will be kept in a password protected folder that will only be accessible by NUNM's Information Technology staff.

16c Implementation

Masking will be accomplished by: using trained staff not involved in trial operations to: 1. Produce the "code" (e.g., X2=XN and Y1=Placebo); 2. Label XN and placebo bottles generically as "X2" and "Y1"; 3. Generating the blocked randomization sequence using Randomization.com; 4. Create 32 sequentially-numbered, sealed envelopes that contain the random group assignments. Upon confirmation of eligibility and interest, Study Coordinators involved with trial operations will then open the next sequential envelope in the stack at the time of randomization, the envelope number will be recorded, and allocation disclosed to both participant and coordinator at that time as simply "X2" or "Y1", indicating which bottles will be dispensed.

17a Blinding (masking)

Triple-masked without PI, Study Coordinator, or Participant knowing participants' allocation assignment.

17b Un-blinding/masking

Un-blinding is permissible if the Data Safety Monitoring Board requires it upon review and in the case of a Serious Adverse Event (SAE).

Data collection, management, and analysis

18a Data collection methods

1. Adverse Events Report Form

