team. Data will be destroyed 3 years after completion of the study. Computer files will be deleted from the server and paper files will be destroyed using a professional document shredding service.

All completed forms will be kept in locked files to which only project personnel have access. These files will also be in locked rooms. Data from paper forms will be manually entered into REDCap and kept as electronic files. Electronic files will be password protected with access given to study personnel only.

28 Declaration of interests

PIs [name] and [name] have received grant support and product donations from Metagenics, Inc. who will be encapsulating the finished product used in this trial. Neither Drs. [name] or [name] hold stock in Metagenics, Inc. or its parent company and have no direct financial ties to the outcome of the proposed clinical research.

29 Access to data

Only the PIs and biostatisticians will have access to study data. All investigators will be masked until the initial data analysis plan has been completed and then PIs will be unmasked as to group assignments. Upon creation of a linkage code document, that document will be physically stored in a signed, sealed envelope by the NUNM Director of Operations ([name]) until it is unsealed at the completion of analyses. A copy of the linkage document will also be created electronically and maintained on the password protected computer, in a password protected file, by the Director of Operations.

30 Ancillary and post-trial care

Unanticipated problems will be recorded in the data collection system throughout the study. The PI will record all reportable events with start dates occurring any time after informed consent is obtained. If participants believe they have suffered an AE related to study procedures, they are welcome to contact us at any time and AEs will be adjudicated. At each study visit, the investigator will inquire about the occurrence of AE/SAEs since the last visit. Events will be followed for outcome information until resolution or stabilization.

31a Dissemination policy

All data produced by the project will be deposited into the appropriate public repository no later than the time of first publication describing the data.

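### The envelope procedure in 16c does not carry out the sex-based blocks of 16a, and two arm-wide bottle codes let one code break expose all 32 participants

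*Protocol*

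**What the plan says.** - **Sequence (16a).** "Randomization will occur in up to 8 blocks of 4 based on biological sex". The block size is fixed at 4. The list is called an initial series.
- **Envelopes (16c).** Staff outside trial operations are to "Create 32 sequentially-numbered, sealed envelopes that contain the random group assignments". The Study Coordinators "will then open the next sequential envelope in the stack at the time of randomization". Neither section mentions a separate female and male series, or choosing an envelope by sex.
- **Bottle codes (16c).** All XN bottles carry one label (X2 in the example) and all placebo bottles the other (Y1). At each randomization the label is shown to both sides: "allocation disclosed to both participant and coordinator at that time as simply" X2 or Y1.
- **Unblinding (17b).** It is allowed when the DSMB requires it and in the case of an SAE. No break limited to one participant is described.
- **Unmasking and custody (16b and 29).** Section 29 says: "All investigators will be masked until the initial data analysis plan has been completed and then PIs will be unmasked as to group assignments". The same section keeps the linkage document sealed until the analyses are complete, in the hands of the Director of Operations. Section 16b restricts the code to Information Technology staff.
- **Planned sex split (15).** The stated aim is half men and half women. Table 3 projects 14 + 3 = 17 women and 13 + 2 = 15 men.

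**The concern.** Blocking by sex works only if each sex has its own sequence. A single stack opened in order of arrival gives blocks that are balanced overall but not within women or within men. The design then names a stratification that its procedure does not perform, and in a trial of 32 the resulting imbalance can be visible.

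The bottle codes raise a different issue. When a whole arm shares one label, the mask is a single secret. Anyone who knows the labels and learns one participant's treatment has decoded every bottle, past and future. The outcomes include ones open to influence by such knowledge. The primary aim counts participants with an adverse event or abnormal laboratory value, adverse events are collected by questionnaire, and the CDAI includes graded pain and subjective wellbeing.

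Section 29 bears on when the mask formally ends. It should give one answer.

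**Working it through.** **1. The plan's own count.** 8 blocks × 4 = 32 envelopes. The sample size section gives the same number: 24 / (1 − 0.25) = 32. The count reproduces.

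**2. Envelopes needed if sex is a stratum.** Blocks = ceil(F/4) + ceil(M/4), with F + M = 32.
- 16/16: 4 + 4 = 8 blocks, 32 envelopes.
- 17/15 (Table 3): ceil(17/4) + ceil(15/4) = 5 + 4 = 9 blocks, 36 envelopes.
- 12/20 or 20/12: 8 blocks. Every other split from 13/19 to 19/13, apart from 16/16, needs 9.

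So 8 blocks suffice only when both totals are multiples of 4.

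**3. Balance among women under one stack.** Assume that all 32 envelopes are used (16 per code) and that the sexes arrive in random order. With K the number of women given X2,

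P(K = k) = C(F, k) × C(32 − F, 16 − k) / C(32, 16),

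and the arm difference is |2k − F|.

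| Women | Distribution of the difference | P(3 or more) | P(5 or more) |
|---|---|---|---|
| 16 | 0: 0.276; 2: 0.435; 4: 0.213; 6: 0.063; 8: 0.011 | 28.9% | 7.6% |
| 17 | 1: 0.521; 3: 0.324; 5: 0.124; 7: 0.028; 9: 0.004 | 47.9% | 15.6% |

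With 16 women only even differences occur, so 3 or more means 4 or more. With sex-specific blocks of 4 the difference within a sex can never exceed 2, because at most one block is incomplete.

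**4. What visible labels and blocks of 4 reveal.** The six possible blocks are XXYY, YYXX, XYXY, XYYX, YXXY and YXYX. An assignment is certain once both slots of the other code are used. That gives 2 certain assignments in each of the first two blocks and 1 in each of the other four: (2 + 2 + 1 + 1 + 1 + 1) / 24 = 8/24 = 33.3%, or about 10.7 of 32. Always guessing the code with more slots left is right with probability 1/2, 2/3, 2/3 and 1 at the four positions, a sum of 2.83 out of 4, or 70.8%. Chance is 50%. These rates assume that staff know the block size (it is printed in the protocol) and keep track of block boundaries. They concern the label. They become statements about treatment only after a code is broken.

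**5. Reach of one code break.** With two labels, decoding one bottle decodes 32 of 32 participants for anyone who knows the labels. With participant-specific kit numbers it decodes 1 of 32.

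**6. Section 29 beside 16b.** One sentence unmasks the PIs when the initial data analysis plan is completed, and another keeps the linkage document sealed until the analyses are complete. If the first means that the plan has been written, the two conflict. If it means that the planned analysis has been carried out, they can agree. The custodian is Information Technology staff in 16b and the Director of Operations in 29, and the protocol does not say whether these are two different documents.

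**The case against.** **Balance.** Table 3 is a projection by race and ethnicity, not a quota. The stated aim is 50/50, which fits exactly 8 blocks and 32 envelopes in two series of 16, and calling the list an initial series leaves room for more. This stands: the 36-envelope figure depends on Table 3, and a site could prepare two series without breaking 16a. It does not remove the gap, because 16c describes one stack and no step by sex. The practical effect is also limited. No subgroup analyses are planned, and sex is a named factor in the longitudinal models.

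**Concealment.** The envelopes are opaque, sealed and signed across the seal, and the code and sequence are made by staff outside trial operations. A reader might infer from the 33% and 71% figures that enrolment can be steered. The documents do not support that without a code break, because until then a predicted X2 has no known direction.

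**Reach of an unblinding.** Section 17b does not say that coordinators or assessors are told the result. Exposure of all 32 is therefore conditional on site staff learning one participant's arm.

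**Other leaks.** A reader might infer that the PIs are unmasked early, or that XN metabolite results give the arm away during follow-up. Neither is established. The Section 29 sentence can mean that the initial analysis has been done, and unmasking at the analysis stage would not make earlier envelopes predictable in any case. No section returns metabolite results to coordinators during follow-up, and Section 29 limits data access to the PIs and biostatisticians.

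**Conclusion.** The point holds in three parts, and it should be settled before envelopes and labels are made.

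- **Sex-based blocks.** As described, they are not carried out. At the 50/50 aim, 28.9% of trials would have an arm difference among women above the cap of 2. At Table 3's projection the figure is 47.9%. Both rest on one stack, full use of 32 envelopes and random arrival order.
- **Shared codes.** Two arm-wide labels are a single point of failure. One decoded participant exposes all 32 to anyone who knows the labels, and fixed blocks of 4 then make about one third of later assignments certain to staff who track the blocks. This is conditional on a code break reaching site staff, which 17b makes possible but does not state.
- **Unmasking time and custody.** The passages do not clearly agree and need to be reconciled.

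**What to change.** - **16a and 16c:** prepare separate female and male envelope series, each with spare blocks, and state that the coordinator opens the next envelope in the series for the participant's sex. Six blocks (24 envelopes) per sex, for example, would cover any split from 8/24 to 24/8, with randomization still stopping at 32.
- **16c and 17b:** replace the two arm-wide labels with unique participant kit numbers. Staff outside trial operations hold the list, so that one code break reveals one participant.
- **16b and 29:** state one unmasking time, after database lock and the primary analysis, and one custodian of the code.

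Mixing in blocks of 2 is not advised. A block of 2 is guessable 1.5/2 = 75% of the time, and an equal number of 2s and 4s gives (1.5 + 2.83)/6 = 72.2%, slightly worse than 70.8% for fixed blocks of 4. Kit numbers remove the visible code and make the change unnecessary.

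The cost is new labels and envelopes, short edits to Sections 16, 17b and 29, and a small one-off amount of staff time.

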Given the small sample size of these clinical trials, results related to changes in inflammatory cytokines (IL-1 β , IL-2, IL-6, IL-8, IL-10, TNF- α , and IL-12p70), gut permeability biomarkers (CD14, intestinal fatty acid binding protein) and markers of endotoxemia (LPS, LPS-binding protein) are considered preliminary, and thus our principle assessment will be measurement of effect size as *Cohen's d* statistic between XN- and placebo-treated groups at each 2-week interval compared to baseline, with the primary comparison being between baseline and week 8. We will also perform formal statistical comparisons as unpaired, 2-sided t-tests (or, if inspection of distributions indicates strong non-normality, with a non-parametric Wilcoxon signed rank test) of the means at relevant time points. The following findings will be considered evidence of possible effects: 1. Clinically and statistically significant effects for changes in cytokines of interest and/or 2. Calculation of a Cohen's d value for effect size estimation greater than 0.5 (with larger d indicating a larger potential effect size).

Assessment for overall *increases* or *decreases* in parameters of interest will be tested for linear trends of the means by linear mixed ANOVA with time point as a repeated factor. Trends will be considered significant if p<0.05 for the model overall.

Analysis of XN, its metabolites, and BAs to determine a small molecule signature of longer-term oral treatment with XN:

We will identify and quantify XN and XN-derived metabolites in plasma, stool, and urine samples. Bile acid profiles will also be determined in the stool samples. The metabolite profile data will then be used for correlation with the time-resolved gut microbiome analysis. This approach will allow us to determine links between metabolite profiles and gut microbiome compositions.

Protocol

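### Section 20a names a paired rank test as the fallback for comparing independent arms, and an unpaired t-test for what reads as a within-person change from baseline

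*Protocol*

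**What the plan says.** Section 8 of the protocol describes a randomized, placebo-controlled trial in which each participant takes either XN or placebo for 8 weeks. Three statements in Section 20a matter here.

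- **Laboratory toxicology, first paragraph.** "All parameters will be evaluated by formally comparing means from baseline" "to each time point by unpaired, 2-sided t-tests, as well as for trends over time". The trends are then to be assessed "by applying linear mixed ANOVA models with time point as a repeated factor". No treatment arm is named in this sentence.
- **Laboratory toxicology, paragraph on changes in distribution.** The plan is "presenting means and confidence intervals (CI) for the change in each group", plus an interval for the difference between groups. Significance is tested by an unpaired two-sided t-test or, under strong non-normality, "with a non-parametric Wilcoxon signed rank test) of the mean values for XN compared to placebo".
- **Cytokines, gut permeability and endotoxemia.** After making Cohen's d between the two treated groups the main assessment, the protocol adds: "We will also perform formal statistical comparisons as unpaired, 2-sided t-tests". The same condition for non-normality follows, "with a non-parametric Wilcoxon signed rank test) of the means at relevant time points".

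The same laboratory measures also get a Fisher's exact comparison of the percentage newly abnormal at each two-week visit. In the omics paragraph, Section 20a names a rank-sum test as a non-parametric alternative.

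**The concern.** A paired test and an unpaired test answer different sampling situations, and Section 20a appears to have them the wrong way round in two places.

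No XN participant is matched to a placebo participant, so there are no pairs for a signed rank test to rank. An analyst following the text would either fail to run it or have to invent a pairing. The choice of test would then be settled after the data are in hand.

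Baseline and later laboratory values come from the same people. An unpaired t-test treats them as two unrelated samples and uses too large a standard error whenever repeated values are positively correlated. Laboratory safety is the primary outcome domain in Section 12. There, a conservative test errs in the uncomfortable direction, because a non-significant result is easily read as reassurance.

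**Working it through.** **1. The plan's own figures.** Section 14 gives, for TNF-α, a mean change of -0.5 on XN and 0.1 on placebo, SD 0.25, 12 per arm, two-sided α 0.05, power above 90%. The difference is 0.6 and the noncentrality is 0.6 / (0.25 × √(2/12)) = 5.88. Power by the noncentral t with 22 degrees of freedom is 99.99%, so the stated figure holds. The enrolment total also holds: 24 / (1 − 0.25) = 32. The TNF-α calculation uses the unpaired t-test between arms, which suits that contrast. No figure in Section 14 uses either test at issue.

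**2. Signed rank between arms.**

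- *Can it be computed?* Only with equal numbers. Section 14 allows for attrition of up to 25%. Assume 16 randomized per arm and independent dropout. The arms then end unequal with probability 1 − Σₖ P(K = k)², where K is binomial(16, retention). This is 84% at 25% attrition and 76% at 10%.
- *If the arms are equal, is the answer determined?* No. In one simulated skewed data set with 12 per arm, 3,000 random pairings of the same values gave signed rank p-values from 0.034 to 1.0 (median 0.38). The rank-sum test gives one value, p = 0.24.
- *Error rates with a pairing fixed blind to outcome.* With 12 per arm and no true difference, signed rank rejected in 4.1–4.4% of simulations and rank-sum in 4.4–4.9%. With a shift of 1 SD (on the log scale for skewed data), power was 50–55% against about 60%.
- *Cytokine paragraph.* Here the t-test is unpaired and its stated alternative is paired, for the same comparison. Whichever contrast is meant, one of the two does not fit. The preceding sentence compares XN with placebo, so the signed rank test is the misfit.

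**3. Unpaired t-test from baseline to a visit.** Let both visits have standard deviation σ and correlation ρ, with n participants and true shift δσ.

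- The variance of the mean change is 2σ²(1 − ρ)/n.
- The unpaired test uses about 2σ²/n, so its standard error is too large by the factor 1/√(1 − ρ).
- The paired test has noncentrality δ / √(2(1 − ρ)/n). For n = 12, δ = 0.5 and ρ = 0.7 this is 0.5 / √0.05 = 2.24. Power by the noncentral t with 11 degrees of freedom is 53%.

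Neither ρ nor δ is in the documents, so both are assumed and ρ is varied. Results from 40,000 simulated arms per cell, n = 12, δ = 0.5:

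| Assumed ρ | Power, unpaired | Power, paired | Actual type I error of the unpaired test (nominal 5%) |
|---|---|---|---|
| 0 | 22% | 20% | 5.0% |
| 0.3 | 18% | 27% | 2.2% |
| 0.5 | 15% | 35% | 0.9% |
| 0.7 | 11% | 53% | 0.2% |
| 0.9 | 6% | 94% | 0.0% |

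With 16 in the arm and ρ = 0.7, power is 17% unpaired and 68% paired.

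**The case against.** The strongest reply is that little depends on these two tests.

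- **Other analyses cover the laboratory data.** Section 20a also plans a mixed ANOVA with time as a repeated factor, intervals for the change within each group, an unpaired XN versus placebo comparison and Fisher's test on newly abnormal values. A reader might infer that safety shifts will be missed. The documents do not support that: one test among several is conservative, and the others can show a shift.
- **The signed rank test is only a fallback.** It applies under strong non-normality, and laboratory values are first checked for skew and transformed. For cytokines, results are called preliminary and Cohen's d leads. A reader might infer that the comparison of XN with placebo is invalid throughout. It is not: the unpaired t-test named first is appropriate. Even the signed rank test keeps its type I error if the arms are equal and the pairing is fixed without regard to outcome. The trouble is that no pairing rule exists.
- **The baseline sentence has another reading.** It may mean change from baseline compared between arms, for which an unpaired test is right.
- **It may be a slip of naming,** since a rank-sum test appears elsewhere in Section 20a.

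The first two points stand and limit the consequence. The third is possible but not the natural reading: the sentence names no arms, treats time as a repeated factor, and leaves XN versus placebo to a later paragraph. At the least, the contrast must be stated. The fourth would explain the error, but the wrong test still stands in two paragraphs.

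**Conclusion.** The point holds in limited form and should be fixed.

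The signed rank fallback is wrong as written for independent arms. This does not depend on any assumption: there are no pairs, and with unequal arms the paired test cannot be run. Its reach is confined to outcomes judged strongly non-normal.

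The unpaired baseline-to-visit test is mis-specified on the natural reading. It is conservative at any positive within-person correlation and can miss shifts. The size rests on a correlation that the documents do not give: there is no loss at 0, a modest loss at 0.3, and a large one from 0.5 upward. A single headline gap in power would therefore overstate what is known.

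The primary hypothesis in Aim 1 (Section 7) counts participants with an adverse event or abnormal laboratory value. Section 14 powers it by a chi-square test, so neither misnamed test touches it.

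**What to change.** Three wording changes in Section 20a:

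1. In both the laboratory paragraph and the cytokine, permeability and endotoxemia paragraph, replace the signed rank test with the Wilcoxon rank-sum (Mann-Whitney) test for XN versus placebo. Keep the unpaired t-test as the main test.
2. In the first laboratory paragraph, state the contrast. For change within an arm, use a paired t-test (signed rank if non-normal) or rely on the mixed model alone. Keep the unpaired test only for change compared between arms.
3. In the cytokine paragraph, say explicitly that the formal test compares change from baseline between arms, if that is what is meant.

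The changes need no extra participants, visits, samples or data. Making them before unmasking avoids choosing a test after the results are known.
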